#### 4.1. Inclusion Criteria

##### **Aim 1 (UCD patients):**

- Age 18 and under
- Diagnosed with the following Neonatal-type urea cycle disorders:
  - o CPSD, OTCD, ASD or ALD, as defined as follows:
    - Diagnosis of CPS I deficiency, defined as decreased (less than 20 % of control) CPS I enzyme activity in liver, and/or an identified pathogenic mutation, and/or hyperammonemia and first-degree relative meets at least one of the criteria for CPS I deficiency
    - Diagnosis of OTC deficiency, defined as the identification of a pathogenic mutation, and/or less than 20% of control of OTC activity in the liver, and/or elevated urinary orotate (greater than 20 uM/mM) in a random urine sample or after allopurinol challenge test, and/or hyperammonemia and first-degree relative meets at least one of the criteria for OTC deficiency
    - Diagnosis of AS deficiency (Citrullinemia), defined as a greater than or equal to 10-fold elevation of citrulline in plasma, and/or decreased (less than 20% of control) AS enzyme activity in cultured skin fibroblasts or other appropriate tissue, and/or identification of a pathogenic mutation in the AS gene, and/or hyperammonemia and first-degree relative meets at least one of the criteria for AS Deficiency
    - Diagnosis of AL deficiency (Argininosuccinic Aciduria, ASA), defined as the presence of argininosuccinic acid in the blood or urine, and/or decreased (less than 20% of control) AL enzyme activity in cultured skin fibroblasts or other appropriate tissue, and/or identification of a pathogenic mutation in the AL gene, and/or hyperammonemia and first-degree relative meets at least one of the criteria for AL Deficiency
  - Willing to participate in at least 1 neurocognitive assessment and 1 quality of life assessment
  - Permit access to medical records and medical providers

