#### **4.4. Retention Strategies**

**Aim 1:** Since this component comprises only 2 visits for neuropsychological testing, we expect a high retention rate among highly motivated patients referred from and enrolled by NUCDF. In comparison, we have observed ~90% retention in the LS protocol since enrollment began in 2006; the LS is more demanding with regard to laboratory and neuropsychiatric testing. UCD appears to affect equally all ethnic groups, except African American, who are underrepresented (~3%). We will make every effort to enroll African American patients in this study.

**Aim 2:** As this component consists of 60-90 minute interviews and/or participation in focus groups, after which subjects exit the study, retention is anticipated to be near 100% (barring the rare occasion when a participant may voluntarily terminate the interview and/or participation in the focus group).

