**Neuropsychological testing and Quality of life questionnaires:**

Neuropsychological tests will be based on age-matched norms for the specific test used (Table 1). These tests overlap with those currently used in the UCDC LS. The findings will be discussed with the participant/parents at the time of the testing, and a report of the results of this testing will be provided to the participant/parent.

Table 1. Validated tests and scales to be used in this study						
Test	Domain	6-35 mo.	3-5 y	6-16 y	≥17 y	Reference
Bayley-II/III	Overall Development (IQ/DQ)	X				[36]
WPPSI-IV			X			[37]
WASI/WASI-II				X	X	[38]
ABAS-II	Adaptive Skills	X	X	X	X	[39]
CBCL	Mood and Behavior		X	X		[40]
BRIEF	Attention/Executive Skills		X	X	X	[41]
TEA-Ch				X		[42]
RCFT				X	X	[43]
TOL-Dx				X	X	[44]
NEPSY	Attention/Executive, Language		X	X		[45]
D-KEFS				X	X	[46]
WRAVMA	Motor		X			[47]
Grooved Pegboard				X	X	
Grip Strength				X	X	[49]
Beery VMI	Visual Motor		X	X		[50]
CVLT-C/II	Learning and Memory		X	X	X	[51]
PedsQL	Quality of Life	X	X	X		[52]
SF-36				X	X	[53]
PROMISE					X	[54-56]

The Quality of Life questionnaires will be administered at the baseline visit to assess the impact the disorder has on the participant's quality of life. Parents of participants aged 1 month to 18 years old will be administered the PedsQL parent-report or parent proxy-report questionnaire. Participants between 13 and 18 years of age will complete the PedsQL child questionnaires for their age group. Adult participants (over 18 years of age) will respond to the SF-36v2 questionnaire and the Patient Reported Outcomes Measurement Information System (PROMIS) questionnaires annually (43, 44). PROMIS questionnaires: Satisfaction with Social Roles and Activities, Cognitive Function (previously called Executive Function), Anxiety, Depression, Emotional/Behavioral Dyscontrol. The site neuropsychologist and/or the site PI will review PROMIS questionnaires within 30 days of administration and follow up with the participant and his/her family, as appropriate, such as if there is any indication that the participant may harm himself/herself or others

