[<http://www.stata.com/stata14/>] to perform analysis of covariance that will enable us to evaluate **Aim 1** outcomes of neurodevelopment and quality of life. Each model will include treatment type, the baseline measurement of each outcome, as well as the CBPS and if necessary the cross product of treatment type by CBPS. When we address survival, we will implement Cox Regression models to predict survival time by treatment and will either control for CBPS or stratify on it in the case of heterogeneity.

We used PASS 12 [33] to evaluate statistical power to address study aims for sample sizes per group (liver transplantation vs. conservative management) of 90 and 80 in 2-tailed testing at an alpha of 0.05, which assumes some losses in the sample entering analysis in order to maintain adequate covariate balance between groups. For neurodevelopmental and quality of life assessments, we have 80% power to detect modest 0.4sd effect size differences between groups assuming two repeated measurements per person correlated at 70% (ICC). For mortality, assuming the rate in the conservatively treated group remains about 28%, the study will have 80% power to detect and increase in the liver transplant group of about 60% which is robust to differences in sample size between 80 and 90 per group. The study is well powered to detect any clinically meaningful difference in neurocognitive outcomes and QOL and adequately powered to detect a moderate difference in mortality between groups.

For **Aim 2**, interview data will be managed using QSR International NVivo 10 software [[http://www.qsrinternational.com/products\\_nvivo.asp](http://www.qsrinternational.com/products_nvivo.asp)], a program that allows us to collect, organize, and code qualitative data sources. Although not explicitly a grounded theory study, our approach to the analysis of primary caretaker and provider interview data will borrow from aspects of Strauss and Corbin's systematic procedures for grounded theory work [34]. No existing framework or theory currently exists that describes the process which UCD patients and their families undertake when making the difficult decision to pursue liver transplant or continue conservative management. Thus, some of Strauss and Corbin's analysis techniques are suitable for this study aim, which seeks to describe a process/experience in a field where there is little pre-existing evidence.

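### The 80% power for a 0.4 SD difference assumes two scores from every one of 80-90 children per group; deaths and missed second tests are not allowed for, and the schedule contains no second assessment

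*Combined protocol and SAP*

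**What the plan says.** **Power (section 6.2).** Power was evaluated for "sample sizes per group (liver transplantation vs. conservative management) of 90 and 80 in 2-tailed testing at an alpha of 0.05", a choice "which assumes some losses in the sample entering analysis in order to maintain adequate covariate balance between groups". For neurodevelopment and quality of life the claim is "we have 80% power to detect modest 0.4sd effect size differences between groups", "assuming two repeated measurements per person correlated at 70% (ICC"). The mortality calculation follows directly, with the same 80-90 per group, "assuming the rate in the conservatively treated group remains about 28" per cent. The paragraph closes by describing the study as having good power for any neurocognitive or quality-of-life difference of clinical importance.

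**Number of assessments.** Sections 4.3 and 4.4 both describe two testing visits; section 4.4 says "Since this component comprises only 2 visits for neuropsychological testing" and cites about 90% retention in the longitudinal study. Section 4.1 asks for less: "Willing to participate in at least 1 neurocognitive assessment and 1 quality of life assessment". Section 4.5, the schedule of events, has only a baseline visit for Aim 1, with neuropsychological testing then or on another date. On quality of life it says "The Quality of Life questionnaires will be administered at the baseline visit". Its only repeat schedule is annual questionnaires for participants over 18, whereas Aim 1 enrols those aged 18 and under.

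**Model (section 6.2).** The neurodevelopment and quality-of-life analyses are longitudinal random-effects regressions that include the baseline value of each outcome.

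**The concern.** The power figure depends on two conditions: two scores per child, and 80-90 analysed children per group. Neither is secured. The second visit appears in the recruitment and retention text but not in eligibility or the schedule, and no interval is given anywhere. The group sizes are reduced from the projected 92 and 93 only for covariate balance. Deaths are a premise of the very next calculation, yet they do not enter this one, and no allowance is made for a missed second test.

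The findings are meant to inform families choosing between transplantation and conservative management. If the study is described as having good power for any difference that matters, a null result is likely to be read as showing no meaningful difference. That reading needs a power figure that reflects the data the study will actually have.

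**Working it through.** **Inputs from the documents.** Two-sided alpha 0.05, difference 0.4 SD, two measurements, ICC 0.7, 90 and 80 per group, conservative mortality about 28% (all section 6.2); projected groups of 92 transplanted and 93 conservatively managed (section 6.1).

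**Formula.** Power = Φ(0.4 / √[v(1/n₁ + 1/n₂)] − 1.96), where v is the variance of a child's outcome in SD² units. For the mean of two scores v = (1 + 0.7)/2 = 0.85; for a single score v = 1.

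**Step 1: reproduce the plan's figure (v = 0.85, complete data).** At 90 against 80: √[0.85(1/90 + 1/80)] = 0.1417; 0.4/0.1417 = 2.824; Φ(2.824 − 1.96) = 80.6%. At 80 per group power is 78.3%, and at 90 per group 82.9%; 84 per group are needed for 80%. The stated figure is therefore a comparison of means of two scores with nothing missing.

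**Step 2: scenarios on the same calculation.** The transplant group is left intact for simplicity. The proportion of deaths that precede completed testing is an assumption, because the documents do not give it.

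| Scenario | Transplant / conservative | v | Power | Difference detectable with 80% power |
|---|---|---|---|---|
| As planned | 90/80; 80/80 | 0.85 | 80.6%; 78.3% | 0.40; 0.41 SD |
| Half of a 28% conservative loss | 90/77; 80/69 | 0.85 | 79.8%; 75.2% | 0.40; 0.42 SD |
| All of a 28% conservative loss | 92/67; 90/65; 80/58 | 0.85 | 77.1%; 76.0%; 71.1% | 0.42; 0.42; 0.45 SD |
| One score each, no deaths | 90/90; 80/80 | 1 | 76.5%; 71.6% | 0.42; 0.44 SD |

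Conservative counts: 90 × 0.86 = 77 and 80 × 0.86 = 69 for half the loss; 93 × 0.72 = 67, 90 × 0.72 = 65 and 80 × 0.72 = 58 for all of it.

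**Step 3: some second scores missing, no deaths.** If a fraction f of children have two scores and the rest one, the effective variance is v = 1/(f/0.85 + 1 − f). At 90 against 80, power is 80.0% for f = 0.9 (the longitudinal study's retention, used here as an assumption about completing the second test), 79.4% for f = 0.8 and 77.5% for f = 0.5.

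**Step 4: the baseline-adjusted model.** If the second score is the outcome and the first is the covariate, with correlation 0.7, then v = 1 − 0.7² = 0.51. Power is 95.4% at 90 against 80, 93.1% at 90 against 65 and 90.1% at 80 against 58. A child with only a baseline score has no follow-up outcome in this model.

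**The case against.** The plan contains no arithmetic error: 80% is the correct answer to the calculation it describes. Two visits are planned, and requiring at least one assessment is an entry minimum, not the intended number. Further scores may come from the longitudinal study, whose data are used, and from past neurodevelopmental testing abstracted at baseline. If most children have two scores, the loss is small (Step 3). All of this stands, so it would be wrong to describe the design as having a single measurement.

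A reader might also infer that the plan's own mortality leaves only 58-67 conservative children for testing. The documents do not support that. It requires every death to precede completed testing and the 80-93 to be counted before deaths, whereas eligibility requires willingness to be assessed and children followed longitudinally may have been tested before they died.

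Finally, the baseline-adjusted analysis would have about 90-93% power even with 58-65 conservative children. That is a fair answer to the mortality part, but it is not the calculation the sponsor reported, and it makes the second score indispensable. It therefore strengthens the point about the schedule.

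**Conclusion.** The concern holds as a power statement with almost no margin for losses the protocol itself anticipates, resting on a second assessment that two sections plan but the schedule and eligibility do not secure. On the plan's mean-of-two calculation, the separate scenarios for deaths and single scores put power between about 71% and 80%, and the detectable difference between about 0.40 and 0.45 SD. The effect is moderate.

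These are scenarios, not expected values or bounds. Stacking a full 28% conservative loss on one score per child gives 64-70%, and a reader might take that as a floor. It is not one: transplant deaths are set at zero, and section 3.3.4 reports mortality of up to 34% in the longitudinal cohort. Nor is it the likely case, since two visits are planned. The true figure depends on the timing of deaths, the number of children with two scores, and which analysis the power refers to, none of which is stated.

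**What to change.** 1. Put the second neuropsychological and quality-of-life assessment, with its interval, into section 4.5, and reconcile it with sections 4.1, 4.3 and 4.4.
2. Restate the power for the number of children expected to have two scores after deaths in both groups, missed second tests and covariate-balance exclusions. Give the assumptions and a range.
3. State whether the power refers to the mean of two scores or to the baseline-adjusted model.
4. Replace the closing claim of good power for any clinically important difference with the detectable difference that results.

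The cost is protocol wording and possibly a less favourable power figure. The second visit is already described in sections 4.3 and 4.4, and no extra enrolment is needed.

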## 3. Background

### 3.1. Overview of Urea Cycle Disorders

[figure not shown]
Urea cycle disorders (UCD) are a group of rare inherited disorders of metabolism caused by deficiencies of any one of eight proteins required for ammonia detoxification and urea synthesis (**Figure 1**) [1]. Collectively, they result in hyperammonemia, which in

its severe or prolonged form may have devastating effects on development and function of the central nervous system [2]. This can manifest soon after birth (neonatal onset) or later in childhood or even adulthood [3]. The variations of severity are most evident in ornithine transcarbamylase deficiency (OTCD) [4], the most common of UCD and the only X-linked disease among them, the rest of which are inherited as autosomal recessive traits. Thus, males with severe OTC deficiency may not survive infancy without vigorous medical intervention and/or liver transplantation [4]. Even with current medical treatment, some evidence suggests that less than 40% of the most severe neonatal cases survive [5]. Males with milder deficiencies may present much later, and females express a range of severity from neonatal onset to being asymptomatic throughout life [4]. Such asymptomatic or mildly affected females represent the largest group within the UCD population, while the more severely affected males and females require the most demanding, intensive, and expensive medical intervention. The classification, abbreviations and estimated prevalence of the various UCD are shown below; as a group, the combined prevalence is approximately 1:35,000 [6].

- N-acetylglutamate synthase (NAGS) deficiency (<1:2,000,000)
- Carbamyl phosphate synthetase I deficiency (CPSD) (1:1,300,000)
- Ornithine transcarbamylase deficiency (OTCD) (1:56,100)
- Argininosuccinate synthase deficiency (ASD, Citrullinemia) (1:250,000)
- Argininosuccinate lyase deficiency (ALD, argininosuccinic aciduria) (1:218,750)
- Arginase (ARG) deficiency (argininemia) (1:950,000)
- Hyperornithinemia, hyperammonemia, homocitrullinuria (HHH) syndrome (or mitochondrial ornithine carrier deficiency-ORNT) (<1:2,000,000)
- Citrullinemia type II (mitochondrial aspartate/glutamate carrier deficiency-CITR) (<1:2,000,000, 1:21,000 in Japanese origin)

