### **3.3.4. Gaps in Knowledge to be Addressed by this Project**

In spite of a number of reports (mostly case reports) on UCD, the mortality rate from these disorders remains uncertain. A mortality rate of up to 50% has been quoted in the literature for patients with neonatal onset UCD [22]. However, we have seen much lower mortality rates among the UCDC longitudinal study cohort (23%-34%) but it is unclear whether this discrepancy reflects a real improvement in the management of UCD during the last two decades or whether there exists an ascertainment bias; an effort is underway in the UCDC to remove survivorship bias and reassess the risk of mortality. Conservative management and liver transplantation are associated with mortality and morbidity, due to hyperammonemia in the former, and peri- and post-surgical complications in the latter. It is, therefore, important that we have information to compare survival as well as other outcomes of the two approaches, taking appropriate account of specific disorders ( a type of UCD) and severity (neonatal or late onset). The second major gap in knowledge is with respect to neurocognitive outcome in patients with UCD. While we have both cross-sectional and longitudinal information about patients with UCD managed conservatively [8, 26], we need more information about patients with UCD who underwent liver transplantation. Our collaboration with SPLIT (Studies of Pediatric Liver Transplantation) will enable us to capture all or most patients with UCD who undergo liver transplantation and thus provide a nonbiased evaluation of their outcomes. The third gap in knowledge is regarding the quality of life in patients with UCD, both those managed conservatively and by liver transplantation. Although being on a restrictive diet contributes to a compliance issue, and has been shown to have a detrimental effect on children's quality of life [27], no comparisons with other treatments have been reported. Last but not least, there is a paucity of evidence

about how patients with UCD, their families, and their providers reach a shared decision on which management strategy to choose, how frequently and by what mechanisms these decisions are revisited, and what clinical, social, and/or system level factors influence this decision process. To date, there have been no published studies that examine the experience of providers or patients with UCD and their families in making this critical and difficult treatment decision.

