## 6.2. Analysis Plan

For **Aim 1**, we will use covariate balancing propensity scoring based on the CBPS package in R [28] to create comparable (balanced) groups based on their risk factor (covariate) profile in subjects according to their propensity (probability) to move from conservative management to liver transplantation. This approach leads to a model that predicts treatment assignment (conservative vs. liver transplantation) and balances covariates, especially those related to study outcome(s), and offers the best opportunity to simulate RCT results from observational data. From prior experience, many through the UCDC [26,31,32], we know many of the important risk factors, which include neonatal vs. late onset, number of prior hyperammonemic events, event severity in terms of hyperammonemic coma score [2], ammonia and glutamine levels at regularly scheduled clinic visits, and duration from birth to transplant or index date. In addition to these, we will consider comorbidities, organ function, and other laboratory assessments. The CBPS software will help us choose the model that maximizes covariate balance and generate the CBPS for each participant. The next steps will be to order the dataset according to the CBPS. It is useful at this point to select CBPS to cut points to form homogeneous strata to assess the number of subjects with a liver transplant and conservative management per stratum. Those strata where there are

insufficient numbers (mismatches) of conservative treatment or liver transplant subjects will be described, documented and excluded from the primary analysis due to lack of covariate balance. Before conducting model-based analyses for **Aim 1**, we will compare survival times based on the log-rank test in Kaplan-Meier analysis and the difference between mean scores based on t-tests by treatment for neurodevelopment and quality of life within each stratum to evaluate evidence of heterogeneity. Evidence of heterogeneity will provide clues to interactive effects based on UCD severity which will be modeled in regression analyses below by including a cross products term of treatment type with CBPS. Based on these results, we will develop general linear random effects longitudinal regression models in STATA 14

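### The 80% mortality power rests on a 28% control rate with no source, time origin or follow-up; it is not shown for survival after the index date, nor does it follow from the plan's inputs as worded

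*Combined protocol and SAP*

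**What the plan says.** Survival is one of the three Aim 1 outcomes. The power paragraph of section 6.2 takes group sizes "of 90 and 80 in 2-tailed testing at an alpha of 0.05", fewer than the 92 and 93 projected in section 6.1, "which assumes some losses in the sample entering analysis in order to maintain adequate covariate balance between groups". It continues "For mortality, assuming the rate in the conservatively treated group remains about 28" per cent, and then "the study will have 80% power to detect and increase in the liver transplant group of about 60" per cent. The paragraph ends by calling the study adequate for a moderate difference in mortality. It does not say where the 28% comes from, from what age or date deaths are counted, or over how long.

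The nearest figure elsewhere is in section 3.3.4, in a discussion of neonatal-onset mortality: "we have seen much lower mortality rates among the UCDC longitudinal study cohort (23%-34" per cent. That section adds that ascertainment bias may be at work and that an effort to remove survivorship bias is still in progress.

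Among the risk factors for the propensity score, section 6.2 lists "duration from birth to transplant or index date". It does not define the index date for a conservatively managed child. Survival is then to be analysed by Cox regression on treatment, controlling for the score or stratified on it.

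**The concern.** A mortality rate can size a survival comparison only if it refers to the same starting point and the same length of follow-up as the comparison. A child who has an index date is alive on that date, so a control death before it cannot enter the comparison. If the 28% includes such deaths, the rate that the analysis can observe is lower than the rate used for sizing. Power for the same relative effect is then lower too. The plan gives the reader no way to tell whether this is so.

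A second gap does not depend on the comparator at all. With 28% taken as given, the stated 80% has to be checked against the stated increase of about 60%.

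The results are meant for families choosing between transplantation and conservative management. If the study is described as adequately powered, a survival result with no clear difference could be taken as evidence of similar mortality when the study had limited ability to show a difference of the stated size.

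**Working it through.** **Inputs.** Control rate 28%, change of about 60%, 80 and 90 per group, two-sided alpha 0.05 (all section 6.2). Cohort range 23%-34% (section 3.3.4), midpoint (23 + 34)/2 = 28.5%.

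**Formula.** Two proportions, normal approximation: power = Φ[(|pT − pC| − 1.96·SE0)/SE1], with SE0 = √(2·p̄(1 − p̄)/n), SE1 = √((pC(1 − pC) + pT(1 − pT))/n) and p̄ the mean of the two rates.

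**Step 1: the plan's own figure, read as a relative increase.** pT = 1.6 × 0.28 = 0.448, difference 0.168, p̄ = 0.364.
- n = 80: SE0 = 0.0761, SE1 = 0.0749; (0.168 − 0.1491)/0.0749 = 0.252; power 60.0%.
- n = 90: SE0 = 0.0717, SE1 = 0.0706; (0.168 − 0.1406)/0.0706 = 0.388; power 65.1%.

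Other methods agree: Schoenfeld log-rank 61.9/67.0%, Freedman 59.4/64.5%, Fisher's exact test 54.0/60.2%. The increase detectable with 80% power is 76% at n = 80 and 72% at n = 90. Reading the 60% as the transplant group's mortality level gives 98.7/99.4%. The stated 80% is not reproduced for an increase.

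**Step 2: read as a relative decrease.** pT = 0.4 × 0.28 = 0.112, difference 0.168, p̄ = 0.196.
- n = 80: SE0 = 0.0628, SE1 = 0.0613; (0.168 − 0.1230)/0.0613 = 0.733; power 76.8%.
- n = 90: SE0 = 0.0592, SE1 = 0.0578; (0.168 − 0.1160)/0.0578 = 0.899; power 81.6%.

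The detectable decrease is 62% and 59%. This fits the plan's 80% and its remark that the result is robust between 80 and 90 per group, but it is the opposite direction to the one written.

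**Step 3: other control rates.** If a share f of the deaths behind the 28% precedes the index date, the rate among those still alive at that date is p = 0.28(1 − f)/(1 − 0.28f). For f = 0.25, p = 0.21/0.93 = 22.6%. For f = 0.5, p = 0.14/0.86 = 16.3%. Both shares are assumptions; f = 0 leaves 28% unchanged. Power is shown for n = 80/90.

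| Control rate | Basis | 60% relative increase | 60% relative decrease |
|---|---|---|---|
| 34% | top of cohort range | 74/79% | 86/90% |
| 28% | plan | 60/65% | 77/82% |
| 23% | bottom of cohort range | 48/53% | 66/72% |
| 22.6% | f = 0.25, assumed | 47/51% | 65/71% |
| 16.3% | f = 0.5, assumed | 33/36% | 49/54% |

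On either reading of the 60%, power falls as the control rate falls. Moving from 28% to the bottom of the cohort range costs about 10 to 12 points, with no assumption about early deaths.

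**The case against.** The strongest reply is that nothing shows 28% to be too high. Section 6.2 attributes it to the conservatively treated group, and no section ties it to the 23%-34% range; closeness to the midpoint is suggestive only. Even if that range is the source, it comes from the Longitudinal Study, which also supplies Aim 1 data. It may count only deaths after enrolment, in which case removing early deaths again would be double counting. All of this stands. It is why the loss is given as a range that includes no loss.

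Three stronger readings are tempting and should not be adopted:
- **Controls are matched at an index age near 12 months.** The 11.7 months in Table 2 (1.5-186) is the surgery age of the transplanted group. Time to index date is one propensity covariate among several, and the control index date is undefined.
- **All controls are alive at enrolment.** The criterion "Willing to participate in at least 1 neurocognitive assessment and 1 quality of life assessment" implies this for new recruits. Section 4.3 says that Longitudinal Study participants are not recruited and that their existing data are used, so deaths after their entry to that study can count.
- **Far fewer deaths are certain.** Section 3.1 does say that "males with severe OTC deficiency may not survive infancy without vigorous medical intervention and/or liver transplantation". That describes one severe subgroup. In Table 2 the controls are 22% OTCD and 77% ASD or ALD (39% + 38%). The documents give no share of deaths before an index date.

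It is also fair to say that the direction of the 60% may be a slip of wording, since a decrease roughly reproduces the 80%. That explains the figure. It does not supply the missing time origin, and power for a decrease also falls with the control rate.

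**Conclusion.** The point holds in a limited form. The 80% power, and the statement that the study is adequate for a moderate mortality difference, are not shown for a comparison that starts at transplant or index date. As worded, they also do not follow from the plan's inputs: a 60% relative increase from 28% has 60/65% power at 80/90 per group. A 60% relative decrease has 77/82%.

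Beyond that, the size is uncertain. At 23% the figures are 48/53% and 66/72%. The 33/36% and 49/54% at a 16.3% control rate rest wholly on the assumption that half of the deaths precede the index date. The documents establish neither that share nor a shortfall of deaths. What they establish is that the rate used for sizing has no stated source, starting point or follow-up, and that the power claim is sensitive to it. The figures use a two-proportion approximation; the log-rank calculations at 28% lead to the same conclusion for the increase.

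**What to change.** In section 6.2:
1. Define the index date for conservatively managed children.
2. Replace 28% with the mortality after that date, over a stated follow-up time, of conservatively managed children in the Longitudinal Study who meet the Aim 1 criteria, and cite that source.
3. Recompute the mortality difference detectable with 80% power at 80-90 per group. State whether it is an increase or a decrease and whether it is relative or absolute, and give a range for the uncertain control rate.
4. Put that figure in place of the closing claim of adequate power for a moderate mortality difference.

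The cost is one query of data the study already plans to use, and a few rewritten sentences. No extra patients are needed. The stated power is likely to be less favourable.
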